3.0 What is/are the hypothesis(es)?

An injection of platelet-rich plasma into the affected gluteus medius tendon will improve pain and function related to this condition with greater efficacy than does injecting whole blood alone.

4.0 Identify and define the primary outcome and when the outcome will be measured. If measuring change in post-operative function is the most important, that will be your primary outcome.

The primary outcomes are improvement in pain, function, and patient satisfaction following platelet-rich plasma or whole blood injection. These outcome measures will be measured via the Numerical Rating Scale for Pain, Non-Arthritic Hip Score, Veterans RAND 12-Item Health Survey, and a 10-cm visual analog scale (VAS) for patient satisfaction which will range from “very dissatisfied” to “extremely satisfied.”

The primary outcome measures will be recorded on day of injection, then 6 weeks, 3 months, 6 months, 9 months, and 1 year post-injection

5.0 Identify and define the secondary outcome(s) and when they will be measured (list additional goals one at a time with their corresponding outcomes).

Secondary outcomes include the Forward Step-down Test (FSD) and patient reported pain during resisted side-lying hip abduction. Patient reported pain during the FSD and resisted side-lying abduction will be measured using a 10-cm visual analog scale (VAS). Other secondary outcomes include any untoward side-effects including increased pain, bleeding, and

infection.

The FSD and resisted side-lying hip abduction outcome measures will be recorded on day of injection, then 3 months, 6 months, and 1 year post-injection.

All other secondary outcome measures will be recorded on day of injection, then 6 weeks, 3 months, 6 months, 9 months, and 1 year post-injection

BACKGROUND - Be sure to answer each question individually

1.0 Explain why these research questions are being asked:

There is no current prospective literature regarding PRP or whole blood injections for the treatment of gluteus medius tendinopathy despite having evidence that these treatments may positively affect tendon healing. It is unknown whether injection with PRP for tendinopathy is more efficacious than injection with whole blood alone. This study may demonstrate efficacy of PRP injections for the treatment of gluteus medius tendinopathy, which would offer patients a potential treatment option prior to the consideration of surgery.

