4. Knee position: if the knee of the tested limb moves medially in the frontal plane and the tibial tuberosity crossed an imaginary vertical line positioned directly over the second toe of the tested foot, 1 point will be given. If the knee moves medially and the tibial tuberosity crosses an imaginary vertical line positioned directly over the medial border of the tested foot, 2 points will be given.
5. Maintenance of a steady unilateral stance: if the patient had to support body weight on the non-tested limb, or the foot of the tested limb moves during testing, 1 point will be given.

A total score of 0 or 1 will be classified as good movement quality, a total score of 2 or 3 will be classified as moderate movement quality, and a total score of 4 or more will be classified as poor movement quality.³⁹

The FSD movements will be recorded neck-down and stored on Citrix ShareFile for future evaluation by a single, blinded investigator.

The patient's pain while performing the FSD will be collected using a Visual Analog Scale.

The patient's pain while performing resisted, side lying hip abduction will also be collected. The patient will be asked to lie on the asymptomatic side, with the hip in approximately 30° of abduction and 5° of extension with their toes pointed downward. One hand of the examiner will be placed on the iliac crest and the other hand will be placed on the lateral portion of the knee. The patient will then be asked to maximally abduct the hip against manual resistance.

Their pain will be recorded following this test using the Visual Analog Scale.

The Forward Step-down Test will be performed pre-injection as well as 3 months, 6 months, and 1 year post-injection. All remaining data will be collected pre-injection and following injection 6 weeks, 3 months, 6 months, 9 months, and 1 year. Questionnaires will be completed either on paper at the time of a normally scheduled office visit, mailed to the study subject in a pre-paid envelope, or online.

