All patients will be required to participate in a structured home exercise program beginning 2 weeks post-injection. In order to ensure standardization for this, all patients will receive two individualized physical therapy sessions with a physical therapist for instruction on these exercises, which will focus primarily on strengthening the hip abductors. Patients will also receive a handout with specific exercise instructions as a guide for their home exercise program. They will also be asked to complete an exercise log in order to help assess

compliance with their home exercise program.

Follow-up study questionnaires on pain, function, and satisfaction will be administered as previously stated.

At 6 months post-injection, the participants who do not report satisfactory improvement will be unblinded, and those who were in the whole blood group will be offered an opportunity to receive a PRP injection for their gluteus medius tendinopathy.

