## **Sample Size Analysis**

Proposed analysis: Two-way repeated measures analysis of variance

Alpha level: 0.01

Beta or power level: 0.864

Number of groups being compared: 2

Effect size or change expected between groups: 15-point change between groups

Resulting number per group: 30

Total sample size required: 72

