## **Data Analysis Plan**

Descriptive analyses of the patient population will include reporting means (with standard deviations) for continuous variables and frequencies (with percentages) for categorical or discrete variables. Independent samples t-test (or non-parametric equivalent) will be used to assess the differences in continuous variables among the two study groups, while chi-square or Fisher's exact test will assess the association between categorical or discrete variables against the study groups. Odds ratio and their 95% confidence intervals will be calculated to measure the strength of that association.

We powered our study to demonstrate an MCID of 15 points in the non-arthritic hip pain score (NAHS) with estimated standard deviation of  $\pm 20$  points. Using that estimate, it was determined that sample sizes of 30 patients in each group achieves 86% power using a two-way repeated measures analysis of variance model with 4 follow-up points and statistical significance set to alpha equal to 0.01. To account for a potential loss-to-follow-up rate of 20%, we plan to increase enrollment for each treatment by 6 patients.

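### The SAP's 86% power is for four NAHS follow-ups, but the protocol schedules five; the SAP should name the visits and the tested term and restate the power

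*SAP*

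**What the plan says.** The SAP's Sample Size Analysis gives "Proposed analysis: Two-way repeated measures analysis of variance", alpha 0.01, power 0.864, a 15-point difference and 30 per group. Its Data Analysis Plan identifies the endpoint as the NAHS with SD 20 and says that "sample sizes of 30 patients in each group achieves 86% power using a two-way repeated measures analysis of variance model with 4 follow-up points". It does not name the four visits, the tested term, the sidedness, the between-visit correlation, or whether SD 20 is for a single visit or for change. The same section assigns independent-samples t-tests to continuous variables without saying how they relate to the powered comparison.

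The NAHS is one of the primary measures. Protocol item 4.0 says: "The primary outcome measures will be recorded on day of injection, then 6 weeks, 3 months, 6 months, 9 months, and 1 year post-injection". Interventions and Observations agrees: "All remaining data will be collected pre-injection and following injection 6 weeks, 3 months, 6 months, 9 months, and 1 year". Both give a baseline and five follow-ups.

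The only four-occasion schedule belongs to the step-down test: "The Forward Step-down Test will be performed pre-injection as well as 3 months, 6 months, and 1 year post-injection". It counts baseline, so it has three follow-ups, and it does not cover the NAHS. (Protocol item 5.0 puts the resisted abduction test on that schedule too, while Interventions and Observations puts it at five follow-ups. This does not affect the NAHS.)

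Interventions and Observations also says: "At 6 months post-injection, the participants who do not report satisfactory improvement will be unblinded", and that "those who were in the whole blood group will be offered an opportunity to receive a PRP injection for their gluteus medius tendinopathy".

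**The concern.** The stated power rests on a number of visits that the protocol does not have for the powered endpoint, so a reader cannot tell which analysis the 86% belongs to.

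Two things depend on this. First, a two-way repeated measures ANOVA has a group term and a group-by-time term, and baseline may or may not be one of its time levels. These tests have different power, and an analyst could follow the SAP as written and run one that was not powered. Second, only three NAHS follow-ups fall at or before month 6. Any set of four therefore includes at least one visit after some participants have been unblinded and some of those in the whole blood group have been offered PRP. The SAP does not say how such values enter the comparison.

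**Working it through.** **Inputs from the SAP:** n = 30 per group, difference 15, SD 20, alpha 0.01, power 0.864, four follow-ups. **Assumptions:** two-sided test, SD 20 at a single visit, and equal correlation ρ between all visits, taken as 0.50 unless shown otherwise.

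**1. Reproducing 0.864.** For the group difference averaged over m follow-ups:

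- variance = 400 × (1 + (m − 1)ρ)/m
- SE = √(variance × 2/30)
- z = 15/SE
- normal power = Φ(z − 2.576)
- exact power = noncentral F with 1 and 58 df and noncentrality z²

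For m = 4 the variance is 400 × 2.5/4 = 250, so SE = 4.082 and z = 3.674. Normal power is 0.864, the stated figure; noncentral F gives 0.840. A one-sided test would give 0.911 (normal), and a single-visit comparison 0.629 (normal) or 0.597 (t). So 0.864 points to a two-sided test of the follow-up average.

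**2. Effect of the visit count (ρ = 0.50).**

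| Follow-ups | Variance | SE | z | Normal | Noncentral F |
|---|---|---|---|---|---|
| 3 | 266.7 | 4.216 | 3.558 | 83.7% | 81.0% |
| 4 | 250 | 4.082 | 3.674 | 86.4% | 84.0% |
| 5 | 240 | 4.000 | 3.750 | 88.0% | 85.7% |

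Over ρ = 0.4 to 0.6, noncentral F power runs from 91% to 80% for five follow-ups and from 86% to 76% for three.

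**3. Baseline as a time level, with the SAP's own four follow-ups (five occasions, ρ = 0.50, noncentral F).** The like-for-like reference is 84.0%.

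- Group main effect: the mean difference is 15 × 4/5 = 12 and the variance is 400 × 3/5 = 240. SE = 4.000 and z = 3.00, so power is 63%.
- Group-by-time, constant step (0, 15, 15, 15, 15): the squared deviations from the mean sum to 180. Noncentrality is 15 × 180/(400 × 0.5) = 13.5 on 4 and 232 df, so power is 65%.
- Group-by-time, even divergence (0, 3.75, 7.5, 11.25, 15): the sum is 140.6 and noncentrality 10.55, so power is 50%.

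**4. Baseline as a covariate.** With an assumed baseline correlation of 0.3, the residual variance is 400 × ((1 + (m − 1)ρ)/m − 0.09). That is 204 for five follow-ups and 230.7 for three. Noncentral t power on 57 df, averaged over chance baseline imbalance, is about 91% and 87%.

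**5. Late visits.** Suppose the difference halves to 7.5 at 9 and 12 months (an illustration, not a forecast). The five-visit mean is then (3 × 15 + 2 × 7.5)/5 = 12. With SE 4.000, z = 3.00 and unadjusted noncentral F power is about 63%, against 85.7% if the full difference persists.

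**6. If SD 20 is the SD of change.** If the equal correlation ρ also covers baseline, and s is the single-visit SD, two changes from the same baseline have variance 2s²(1 − ρ) and covariance s²(1 − ρ). They correlate 0.50 whatever ρ is. The unadjusted figures at 0.50 then hold for change scores, and the covariate figures in step 4 do not.

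**The case against.** The strongest defence is that the count is nearly harmless. A calculation that uses fewer repeats than will be collected is conservative: on the SAP's apparent method, moving from four to five follow-ups raises power from 86.4% to 88.0%. That stands. A reader might infer from the mismatch that the 86% is wrong or that the trial is too small. The documents do not support this, because the figure reproduces and the scheduled visits give slightly more power.

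A reader might also take 50% to 65% as the real power of the plan. That does not follow either. Those figures need baseline as a time level, whereas the SAP speaks of follow-up points, which most naturally excludes baseline, and 0.864 matches the follow-up average. They show what is at stake if the term stays unnamed.

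A third objection is that a baseline covariate goes beyond reconciling a visit count, and that the baseline correlation of 0.3 has no source. The second part stands, so the adjusted figures are illustrations only. The covariate is still worth specifying: it settles the role of baseline and uses data already collected. If baseline carried no information the cost would be small (84.9% against 85.7% for five follow-ups at ρ = 0.50).

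Finally, the 6-month provision should not be read as unblinding everyone. It applies to participants whose improvement is unsatisfactory, and the PRP offer to those of them in the whole blood group. How far it would shrink the late difference cannot be derived from the documents.

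**Conclusion.** The point holds as a mismatch and a specification gap, not as a shortfall in sample size. The SAP's power is for four NAHS follow-ups, the protocol has five, and no set of four is defined. By the same method, five against four is worth about +2 percentage points and three against four about −3. The unnamed term is the larger uncertainty: 84.0% for the follow-up average against 63%, 65% or 50% under the three baseline-as-time-level readings, all by noncentral F with four follow-ups. Which visits are analysed also matters beyond their number, since the five-visit figure assumes that the 15-point difference persists after month 6. All figures rest on an assumed correlation of 0.50, a two-sided test, 30 per group and SD 20 at a single visit. The change should be made before the analysis, but it does not call the trial's size into question.

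**What to change.** In both SAP sections, replace the reference to four follow-up points with the NAHS visits to be analysed, reconciled with the protocol's visit schedule and its 6-month provision. Then state the following.

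- **Powered comparison:** the between-group NAHS difference averaged over the named follow-ups, in a repeated-measures model with baseline NAHS as a covariate and not a time level. Say that this, and not the t-test, is the powered test.
- **Power, by noncentral F:** 30 per group, 15 points at each analysed visit, single-visit SD 20, two-sided alpha 0.01, assumed between-visit correlation 0.50. Unadjusted, it is 86% for all five follow-ups (91% to 80% over correlation 0.4 to 0.6), or 81% for the three through 6 months (86% to 76%). At an assumed baseline correlation of 0.3, the adjusted figures are about 91% and 87%.
- **Late visits:** if 9 and 12 months are included, say how values after the unblinding and PRP offer are handled, and that the five-visit figure assumes the full difference persists. Unadjusted power would be about 63% if the late difference halved.
- **SD:** if 20 is the SD of change, say so. The unadjusted figures at 0.50 then apply to change scores and the covariate figures do not.

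The cost is SAP wording and a rerun of the power calculation. No patients, visits or data are added, and enrolment stays at 72 for this test. The stated power may move a few points, partly because noncentral F replaces the normal approximation (84.0% against 86.4% for the same four visits).

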A prospective study evaluating the efficacy of autologous whole blood injection to treat tendinopathy of lateral epicondylitis demonstrated significantly positive results with regard to pain, satisfaction, and ultrasound morphology of the affected tendon.¹¹ While PRP is more commonly used for injection therapy in tendinopathy, the extent to which PRP is more efficacious than whole blood remains unclear due to lack of high quality prospective studies comparing these two treatments.

Extrapolating from current research, this study seeks to advance PRP research with a double-blind randomized trial comparing autologous PRP versus whole blood injection to treat GTPS due to gluteus medius tendinopathy. It will also provide evidence to guide management for GTPS in cases refractory to more conservative treatment options.

Study Design

Experimental:

Name	Description
Randomized Controlled Clinical Trial	This is the “gold standard” for clinical research. These prospective studies have at least two groups. Patients meeting strict inclusion/exclusion criteria are enrolled and randomly assigned to receive either an experimental intervention or to receive what is considered to be an acceptable alternative – usually the current standard of care or a placebo (e.g., study of hyaluronic acid injection versus cortisone for arthritis).

Recruitment

1.0 Check all that apply to describe your study population:

Population
Patients

2.0 Inclusion Criteria:

- Moderate to severe lateral hip pain for greater than 3 months
- Symptoms are refractory to conservative treatment, including at least 8 weeks of traditional physical therapy for this condition
- Moderate to severe gluteus medius tendinosis with or without partial tear <1cm
- Normal neurologic exam except for hip abductor weakness on the affected side.

3.0 Exclusion Criteria:

- Severe (Tennis grade >1) hip osteoarthritis with active synovitis or bone edema
- Active lumbar radiculopathy with pain, numbness or weakness in a dermatomal distribution.
- No evidence of fatty atrophy, denervation, or complete tears of gluteus medius seen on MRI.
- Any condition that requires anti-platelet or anti-coagulation therapy, including aspirin therapy for cardiac conditions
- Non-English Speaking

4.0 Age Range:

30-65 years

Target Enrollment

1.0 * What is the maximum number of subjects you plan to enroll in this study at HSS?(Please enter a number)
72

Interventions and Observations

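### Six extra patients per arm cover a loss to follow-up of 16.7%, not the stated 20%

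*SAP*

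**What the plan says.** The SAP's Data Analysis Plan bases the sample size on a 15-point difference in the Non-Arthritic Hip Score with a standard deviation of 20, four follow-up points and alpha 0.01. It reports that "sample sizes of 30 patients in each group achieves 86% power". The Sample Size Analysis list agrees: "Beta or power level: 0.864" and "Resulting number per group: 30".

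The allowance for attrition is one sentence in the Data Analysis Plan: "To account for a potential loss-to-follow-up rate of 20%, we plan to increase enrollment for each treatment by 6 patients". Thirty plus six is 36 per arm, which matches the list's last line, "Total sample size required: 72". The protocol, under Target Enrollment, also gives 72 as the "maximum number of subjects you plan to enroll in this study".

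Neither document makes any other allowance for loss. Neither says that the 20% is to be taken on any base other than the patients enrolled.

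**The concern.** A loss-to-follow-up rate is ordinarily a fraction of the patients enrolled. To finish with a required number, that number is divided by one minus the rate. The SAP's six patients per arm are 20% of 30, so the required number appears to have been multiplied by 1.20 instead of divided by 0.80. The two operations do not give the same answer, and multiplying gives the smaller one.

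At stake is whether the stated power survives the attrition that the plan itself anticipates. A reader of the SAP would conclude that 86% power still holds if one patient in five is lost. On the plan's own figures, the expected number of completers is then below the number to which that power is attached.

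**Working it through.** **Inputs from the SAP.** Required number per group 30; power 0.864; alpha 0.01; difference 15; SD 20; four follow-up points; loss 20%; six added per arm.

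**Inputs not stated, so assumed.** A two-sided test (an F test of two groups is equivalent to one); a comparison of group means averaged over the four visits; compound symmetry with between-visit correlation ρ. These matter only for the power figures. The enrolment arithmetic does not use them.

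**1. Reproducing the plan's enrolment.** 30 × 1.20 = 36 per arm; 2 × 36 = 72. This matches.

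**2. What 36 per arm allows.**
- Completers after 20% loss: 36 × 0.80 = 28.8 per arm, or 72 × 0.80 = 57.6 in total.
- Shortfall against 30: 1.2 per arm, 2.4 in total.
- Largest loss that leaves 30: 6/36 = 16.7%.

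**3. What a 20% loss requires.** 30/(1 − 0.20) = 37.5, rounded up to 38 per arm, 76 in total. Check: 38 × 0.80 = 30.4, while 37 × 0.80 = 29.6 is still below 30.

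**4. Reproducing the plan's power.** The variance of a patient's mean over m visits is SD² × [1 + (m − 1)ρ]/m. With m = 4 and ρ = 0.50 this is 400 × 2.5/4 = 250. The standard error of the group difference is √(2 × 250/n), and power is approximately Φ(15/SE − 2.576).
- n = 30: SE = 4.082, 15/SE = 3.674, power 0.864. This matches the SAP.

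The value ρ = 0.50 was chosen because it returns 0.864; the SAP gives no correlation. A noncentral F calculation returns 0.864 at ρ = 0.453.

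**5. Power after the loss, if lost patients contribute nothing.**

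| Completers per arm | Normal approximation, ρ = 0.50 | Noncentral F, ρ = 0.453 |
|---|---|---|
| 30 | 0.864 | 0.864 |
| 29 | 0.850 | 0.849 |
| 28.8 | 0.847 | 0.846 |

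The fall is 1.7 to 1.8 percentage points. It depends little on the unstated details: an F test with 3 numerator degrees of freedom (as for a group-by-visit interaction over four visits), calibrated to 0.864 at 30, gives about 0.845 at 28.8.

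**6. When the power loss disappears.** Both cases use the normal approximation with ρ = 0.50.
- All five post-injection visits listed in the protocol are used: the variance is 400 × 3/5 = 240, and power at 28.8 per arm is 0.864.
- Each lost patient contributes one visit: information per arm is 28.8/250 + 7.2/400 = 0.1332, the standard error is √(2/0.1332) = 3.875, and power is 0.902.

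**7. Chance variation.** If each patient has an independent 20% risk of loss, an arm of 36 ends with fewer than 30 completers with probability 0.60. With 38 per arm the probability is 0.34, so only part of the 0.60 is due to the allowance.

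**The case against.** The arithmetic is not in dispute; the case against concerns its weight.

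- **A 20% uplift.** If 20% means an uplift on the 30 required, 30 × 1.20 = 36 is exact, and the sentence does not expressly promise that 30 will remain. But that is not what a loss-to-follow-up rate ordinarily means, and neither document defines it so. If it was intended, the text still needs to say so.
- **Small effect.** The gap is two patients per arm and less than two points of power, with power well above 80%. This stands, and it is why the point is minor. Four patients in total (72 against 76) is nevertheless more than rounding.
- **Conditional power loss.** The correlation was chosen to return 0.864, so the match does not confirm the sponsor's method, and the loss vanishes with a fifth visit or with partial data from lost patients. This also stands. However, the SAP powers on four visits and gives no rule for missing data, and a classical repeated measures analysis of variance usually drops incomplete patients.
- **A reviewer's power figure in the SAP.** The sponsor should confirm about 85% with its own correlation before adopting it. Any F test calibrated to 0.864 at 30 gives much the same figure, so a material change is unlikely.

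**Conclusion.** The concern holds, as a minor error. Six extra patients per arm allow for a 16.7% loss. At the stated 20%, the expected number completing is 28.8 per arm, 1.2 below the number on which the power figure rests. This follows from the SAP's own numbers, given only that the loss rate is a share of patients enrolled.

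The effect on power is a fall from 86.4% to about 85%. That rests on lost patients contributing no data, a two-sided test at 0.01 and compound symmetry over four visits. It could be nil if the analysis uses all five post-injection visits or retains partial data, but the SAP commits to neither. Nothing here calls the trial's design into question.

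**What to change.** Keep enrolment at 72 and replace the attrition sentence in the SAP's Data Analysis Plan with text such as:

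> Enrolling 36 per arm (72 in total) leaves 30 per arm, and so the stated power, for loss to follow-up of up to 16.7%. At 20% loss about 29 per arm complete, giving about 85% power, assuming a between-visit correlation of [value used].

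The sponsor should fill in the correlation and confirm the 85% from its own calculation. In the Sample Size Analysis list, label 30 as the number completing per group and 72 as the number to enrol.

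The cost is one sentence and two labels, with no change to enrolment or analysis. The stated power at 20% loss becomes about 1.7 points lower. The alternative is to enrol 38 per arm (76 in total), which keeps 30 per arm at 20% loss but exceeds the protocol's maximum of 72. The size of the error does not require it.

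### The only longitudinal analysis named is a repeated-measures ANOVA with four unnamed visits and no missing-data method; in its classical form it discards early scores and, if unimproved patients leave unequally by arm after month 6, can bias the comparison toward PRP.

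*SAP*

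**What the plan says.** The SAP's Sample Size Analysis gives "Proposed analysis: Two-way repeated measures analysis of variance". Its Data Analysis Plan repeats this in the power statement, as a "two-way repeated measures analysis of variance model with 4 follow-up points", without saying which visits the four are. Loss to follow-up appears once: "To account for a potential loss-to-follow-up rate of 20%, we plan to increase enrollment for each treatment by 6 patients". In the text available, neither document names an analysis population, a rule for missed visits, a sensitivity analysis, or the handling of scores obtained after unblinding.

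Protocol section 4.0 schedules the primary outcomes at baseline and at five post-injection visits: 6 weeks and 3, 6, 9 and 12 months. Under Interventions and Observations, 1.0, all participants without satisfactory improvement are unblinded at 6 months, and "those who were in the whole blood group will be offered an opportunity to receive a PRP injection for their gluteus medius tendinopathy". No corresponding offer to unimproved PRP participants is stated.

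**The concern.** Extra recruitment replaces numbers. It does nothing about which patients are missing, or about scores already collected from those who leave.

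A classical repeated-measures ANOVA needs a complete row for each patient, so one missed visit removes all of that patient's scores. The 6-month rule could make this unequal between arms. An unimproved whole-blood patient learns that another treatment is on offer; an unimproved PRP patient learns that PRP has already been given. If the second kind of patient leaves more often and a 9- or 12-month visit is in the model, the analysis loses PRP failures together with their blinded 6-week, 3-month and 6-month scores.

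At stake are the validity of the comparison at visits where the randomised contrast was still intact, and the false-positive rate. Even if drop-out is balanced, data are wasted.

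This differs from the question of what post-switch scores mean. Here the damage would be to scores obtained before any switch.

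**Working it through.** **Inputs from the SAP.** "Alpha level: 0.01" (taken as two-sided), "Beta or power level: 0.864", a 15-point NAHS difference, SD 20, 30 per arm raised to 36, four follow-up points.

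**Assumed.** Correlation 0.5 between any two visits; no true difference; departure after month 6 depends on the month-6 score. The share unimproved is varied from 20% to 50%. The only related figure in the documents is 2 of 10 in the centre's retrospective PRP series (Protocol, Background 2.0).

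**1. The plan's own power.** SD of a four-visit mean = 20 × √((1 + 3 × 0.5)/4) = 15.81. SE with 30 per arm = 15.81 × √(2/30) = 4.08. Power = Φ(15/4.08 − 2.576) = 0.864. This matches the SAP, so 0.5 is a reasonable working correlation, although the SAP does not state one.

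**2. Which visits.** Three of the five post-injection visits are at or before month 6. Any four must therefore include month 9 or month 12. Only a count that includes baseline (baseline, 6 weeks, 3 and 6 months) avoids this.

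**3. Bias in a completers-only analysis.** Let f be the share unimproved (the lowest f of month-6 scores), p the share of those who leave, and φ(z_f) the normal density at that cut.

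- Bias at month 6 = 20 × p × φ(z_f)/(1 − pf).
- Averaged over four visits, multiply by (1 + 3 × 0.5)/4 = 0.625.

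Only unimproved PRP patients leave:

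| f | p | Month 6 | Four-visit mean |
|---|---|---|---|
| 0.20 | 0.25 | 20 × 0.25 × 0.280/0.95 = 1.47 | +0.9 |
| 0.20 | 0.50 | 20 × 0.50 × 0.280/0.90 = 3.11 | +1.9 |
| 0.40 | 0.50 | 20 × 0.50 × 0.386/0.80 = 4.83 | +3.0 |
| 0.50 | 0.50 | 20 × 0.50 × 0.399/0.75 = 5.32 | +3.3 |

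Simulated trials with 36 per arm agree, reaching +3.4 in the last row. Rejection rates at nominal 0.01 are about 0.012 in the first row, 0.02 in the second and 0.04 in the last, nearly all in favour of PRP in the last three rows.

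The pre-switch visits alone are shifted too. Over 6 weeks, 3 and 6 months the factor is (1 + 2 × 0.5)/3 = 0.667, giving +2.1 (3.11 × 0.667) and +3.2 (4.83 × 0.667) in the second and third rows. In such runs at f = 0.20 and 0.40, a likelihood analysis of all observed visits had bias within about 0.1 point.

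**4. Sensitivity of that bias.**

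- A quarter of unimproved whole-blood patients also leave: f = 0.20 gives (3.11 − 1.47) × 0.625 = +1.0; f = 0.50 gives (5.32 − 20 × 0.25 × 0.399/0.875) × 0.625 = (5.32 − 2.28) × 0.625 = +1.9. Error rate about 0.012 to 0.017.
- In addition, an assumed 15-point gain at the last visit in unimproved whole-blood patients who stay: subtract (15/4) × their share. f = 0.20: 3.75 × 0.15/0.95 = 0.59, leaving +0.4. f = 0.50: 3.75 × 0.375/0.875 = 1.61, leaving +0.3. Error rate close to 0.01.

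**5. Precision with balanced 20% drop-out.** If leavers give k follow-up scores, the completers-only variance divided by the all-visits variance is 1/(1 − 0.2R²), with R² = 0.625k/(1 + 0.5(k − 1)).

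- k = 0: R² = 0, ratio 1.00.
- k = 1: R² = 0.625, ratio 1/0.875 = 1.14.
- k = 2: R² = 0.833, ratio 1/0.833 = 1.20.
- k = 3: R² = 0.9375, ratio 1/0.8125 = 1.23.

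Completers' SE = 15.81 × √(2/28.8) = 4.17, where 28.8 = 36 × 0.8. With k = 3 and all visits used it is 4.17/√1.23 = 3.76.

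**The case against.** A reader might infer that the SAP deletes patients with a missed visit. It does not say so. Deletion is a property of the classical method, and a repeated-measures model fitted by likelihood would keep partial data. That objection stands as to wording, but the SAP names no such version, so nothing rules out the classical one.

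A reader might also infer that the result will favour PRP. The documents do not support that. They give no drop-out rate by arm, and a motive to leave is an inference from an offer made to one arm. Staying is also easy: Interventions and Observations, 1.0 allows questionnaires to be mailed in a pre-paid envelope or completed online, and the NAHS is a questionnaire. The direction in step 3 follows from having only PRP patients leave and giving the switch no effect; step 4 shows that modest changes to equally unsupported assumptions nearly remove the shift. The calculation also equates a patient's own report of unsatisfactory improvement with a low NAHS score.

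If the four points run from baseline to month 6, departures after month 6 do not affect the ANOVA and the arm-specific mechanism disappears. Patients lost earlier would still forfeit their scores.

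On precision, the extra recruitment covers most of the loss: 28.8 completers give SE 4.17 against the planned 4.08. Discarding usable scores is still avoidable.

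**Conclusion.** The concern holds as a conditional risk. The plan names a method that, in its classical form, needs complete data; it leaves the visits unnamed; and it meets loss only with more patients. Any four post-injection visits extend past an unblinding that treats unimproved patients differently by arm.

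If unimproved PRP patients leave more often than unimproved whole-blood patients, the completers-only contrast is shifted by about +1 to +3.4 NAHS points toward PRP, and the error rate is about 0.012 to 0.04 rather than 0.01. This rests on SD 20, correlation 0.5, no true difference, no effect of the switch, and assumed departure rates. It falls toward zero if whole-blood patients also leave or switched patients gain, so neither a definite bias toward PRP nor a definite inflation of the error rate can be claimed.

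The precision loss needs no imbalance. It is 0 to 23% in variance, and about 14 to 23% where leavers gave at least one follow-up score.

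**What to change.** In the SAP's Sample Size Analysis and Data Analysis Plan:

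- Name the analysed visits.
- Replace the ANOVA with a linear mixed model for repeated measures: visit as a category, group-by-visit terms, and a pre-specified covariance (for example unstructured). Include every randomised patient in the assigned group with all observed visits.
- State that scores up to month 6 are kept whatever happens later.
- Base the PRP versus whole-blood contrast on visits up to month 6, and state how scores after a switch are treated. Using all visits without such a rule would mix the two treatments in the whole-blood arm.
- Report withdrawals after month 6 by arm and by improvement status.

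The cost is SAP wording and a standard model; no visit, treatment or patient number changes. The model assumes that missing scores are predictable from observed ones. That can fail, but it is a weaker assumption than the complete-case analysis makes.
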